5.2.4.3 Secondary efficacy analyses

Secondary efficacy analyses will be performed on the FAS population except if otherwise specified.

5.2.4.3.1 *SRI response*

The SRI-4, 6, 8, 10 responses will be described at Week 36. (Statistical tables 14.2.5.1, 14.2.5.4, 14.2.6.1, 14.2.7.1, 14.2.8.1)

The SRI-4 response (section 4.1.2.1) will be analyzed using the same method as the primary analysis for the second co-primary endpoint (logistic regression). This analysis will be performed both on the FAS and PP sets. (Statistical tables 14.2.5.2 & 14.2.5.5)

The model on FAS for patients IFN-K treated with the status of IFN α neutralizing antibodies (positive/negative) at Week 36 as dependent variable will be also presented (Statistical table 14.2.5.3).

The SRI-6, 8, 10 responses to treatment at week 36 will also be analyzed using a logistic regression using the response rate as dependent variable and treatment as independent variable, while adjusting for the minimization factors used for randomization. (Statistical tables 14.2.6.2, 14.2.7.2, 14.2.8.2)

All analyses performed on SRI-4 will also be conducted on the composite SRI-4 (both with tapering CS \leq 5 mg and \leq 7.5 mg) on the FAS population only. (Statistical tables 14.2.5.6 to 14.2.5.11)

The SRI-4 response is an important and alternative endpoint assessing the clinical response. In case, there will be no trend on the BICLA response, the SRI-4 response could be chosen as primary endpoint for further development of IFN-K.

5.2.4.3.2 *SLEDAI response*

Number of patients achieving a SLEDAI response, defined as a reduction of the SLEDAI-2K score of at least 4 points at Week 36 compared to baseline will be analyzed using frequency table methods (Statistical table 14.2.9).

SLEDAI-2K score at each visit and change from baseline by treatment group will also be presented (Statistical tables 14.2.10.1 to 14.2.10.2).

All SLEDAI data will be listed in Listing 16.2.6.2.

5.2.4.3.3 *BILAG*

Shift tables between Baseline and LVA (last available value between Week 36 and Week 24) will also be presented for each body system. (Statistical table 14.2.11)

Finally, descriptive statistics for the BILAG global score at each visit and change from baseline to LVA will be presented. The difference between treatment groups for the change from baseline to LVA will be analyzed using the non-parametric Wilcoxon-test. (Statistical table 14.2.12)

Statistical Analysis Plan

Study Name: IFN-K-002

SAP version & date: v4, 18/Jun/2018

The BILAG global score will be defined as the summation of the numerical values for the nine-system scores as given by the following formula:

$$\text{Numerical global score (xs)} = A*12 + B*8 + C*1$$

Where A, B and C represent the number of Grades A, B and C respectively at each assessment. Grades D and E are considered as 0 (Chee-Seng Yee *et al*, 2010).

All BILAG data will be listed in Listing 16.2.6.3.

5.2.4.3.4 *SELENA SLEDAI flare index*

The numbers of patients with a mild or moderate, or severe SLE flare (SELENA-SLEDAI flare index) and corresponding number of SLE flare will be presented. (Statistical table 14.2.13).

The total score at each visit (planned in the protocol) and change from baseline by treatment group will also be presented. The change at Week 36 will be analyzed using a t-test. (Statistical tables 14.2.14.1 to 14.2.14.2).

All SELENA-SLEDAI flare index data will be listed in Listing 16.2.6.4.

5.2.4.3.5 *SLICC/ACR-DI*

Total score at each visit and change from baseline by treatment group will be presented. The change at Week 36 will be analyzed using a t-test. (Statistical tables 14.2.15.1 to 14.2.15.2).

All SLICC/ACR-DI data will be listed in Listing 16.2.6.5.

5.2.4.3.6 *CLASI*

Total activity score and Total damage score at each visit and change from baseline by treatment group will also be presented. The changes at Week 36 will be analyzed using a t-test. (Statistical tables 14.2.16.1 to 14.2.17.2).

All CLASI data will be listed in Listing 16.2.6.6.

5.2.4.3.7 *LLDAS*

Number of patients achieving a LLDAS at Week 36 will be presented by treatment group (Statistical table 14.2.18). It is defined as:

- SLEDAI-2K ≤ 4 , with no activity in major organ systems (renal, CNS, cardiopulmonary, vasculitis, fever) and no haemolytic anaemia or gastrointestinal activity
- No new features of lupus disease activity compared with the previous assessment (New feature is defined as any BILAG item recorded as "new" (modality 4) at Week 36)
- Physician global assessment (PGA, scale 0–3) ≤ 1
- Current prednisolone (or equivalent) dose ≤ 7.5 mg daily (this criterion will be identified by medical review)
- Well tolerated standard maintenance doses of immunosuppressive drugs and approved biological agents, excluding investigational drugs (this criterion will be identified by medical review)

Statistical Analysis Plan

Study Name: IFN-K-002

SAP version & date: v4, 18/Jun/2018

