11.2 Eligibility Criteria

All applicable **inclusion** and **exclusion** criteria as described in Sections 8.3 must be checked after informed consent has been given at the Screening Visit (Visit 1, Week -4 to 0) and again at Visit 2 (Week 0) before randomization.

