3.3 Analysis dataset definitions

3.3.1 Full Analysis Set (FAS)

The primary efficacy analysis population is the Full Analysis Set (FAS). It will include all randomized patients who received at least one dose of the study product (IFN-K or placebo). This population will be analyzed according to the result of the random treatment assignment.

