4.1.2 Secondary efficacy endpoints

4.1.2.1 Clinical Secondary Endpoints

- Response to treatment with IFN-K, as measured by the SLE Responder Index (SRI)-4 response criteria at Week 36:
 - Reduction \geq 4 points in SELENA-SLEDAI at week 36 compared with baseline
and
 - No new BILAG A at Week 36
and
 - No more than 1 new BILAG B at Week 36
and
 - No deterioration at Week 36 in PGA (< 10% worsening) on VAS 100 mm compared with baseline
- Response to treatment with IFN-K, as measured by the composite SLE Responder Index (SRI)-4 response criteria at Week 36:
 - Same criteria as above
and
 - Sustained reduction in oral corticosteroids (\leq 5 mg and \leq 7.5mg/day) at Week 36 (these criteria will be identified by medical review)
- Response to treatment with IFN-K, as measured by SLEDAI response, defined as a reduction of the SLEDAI-2K score of at least 4 points at Week 36 compared to baseline
- Response to treatment with IFN-K, as measured by BILAG grade changes by body system
- Response to treatment with IFN-K, as measured by Incidence of SLE flare (SELENA SLEDAI flare index. BILAG flares)
- Response to treatment with IFN-K, as measured by SLICC/ACR-DI
- Response to treatment with IFN-K, as measured by Cutaneous LE Disease Area and Severity Index (CLASI)
- Response to treatment with IFN-K, as measured by LLDAS (Franklin *et al*, 2016)

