5.3.8 Examination of Subgroups

No subgroups have been defined.

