5.4 Data handling conventions

5.4.1 Baseline definitions

For IFN gene signature, only Week 0 (visit 2) will be considered as baseline.

For BILAG scores, a baseline value will be defined for each body system. This baseline will be the value at Week 0 (visit 2).

For other efficacy and safety endpoints the last observation prior to the first dose of study treatment administration will be used as the baseline value. This will usually correspond to the measurement performed at Week 0 before first-dose. However, in case of missing value at Week 0, the last available value recorded during screening will be used as baseline value.

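### SRI-8 and SRI-10 are analysed only in the whole FAS, where eligible patients with baseline scores of 6–7 or 6–9 cannot respond; an analysis restricted by baseline score should be added

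*SAP*

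**What the plan says.** SAP 5.2.4.3 sets the default population: "Secondary efficacy analyses will be performed on the FAS population except if otherwise specified". For the higher thresholds, 5.2.4.3.1 says "The SRI-6, 8, 10 responses to treatment at week 36 will also be analyzed using a logistic regression", with treatment as the explanatory variable "while adjusting for the minimization factors used for randomization". It makes no exception to the default set for these thresholds. The FAS (SAP 3.3.1) takes in everyone randomised and dosed at least once, whatever the baseline score.

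The minimisation factors are ethnic origin, age group, renal BILAG, and corticosteroid, hydroxychloroquine and MMF use. Baseline disease score is not among them. SAP 5.3.1 adds a baseline value to the MMRM only. On subgroups, SAP 5.3.8 says "No subgroups have been defined".

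SAP 4.1.2.1 defines only SRI-4, whose score component is a fall of at least "4 points in SELENA-SLEDAI at week 36 compared with baseline". For SRI-6, 8 and 10, falls of at least 6, 8 and 10 are implied. Under SAP 5.4.1, "the last observation prior to the first dose of study treatment administration will be used as the baseline value", which is usually the Week 0 value.

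Protocol 8.3.1 requires a SLEDAI of at least 6 (the synopsis specifies SLEDAI-2K). Protocol 11.2 has eligibility checked at screening "and again at Visit 2 (Week 0) before randomization".

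**The concern.** SELENA-SLEDAI is a sum of positive weights and cannot fall below zero. A patient who starts at 6 or 7 cannot lose 8 points, and one who starts at 6 to 9 cannot lose 10. The entry rule admits both. In the planned analysis they are certain non-responders in both arms and carry no information about treatment on that endpoint.

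Two things follow. The reported response rates mix patients who did not respond with patients who could not, so the absolute difference understates the effect in those able to show one. Some power is also given up. The secondary objective is SRI-4 and above (Protocol 6.2, SAP 2.2.2), so the higher thresholds are there to be read. The same objectives already limit CLASI to patients with skin lesions at baseline, which is the logic needed here.

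**Working it through.** **The plan's own figure.** The documents give no rate, power or sample size for SRI-6, 8 or 10. The only binary calculation is for BICLA (Protocol 13.1): 20.6% vs 40.6%, 80 evaluable per arm, two-sided 5%, power 73%. The two-proportion formula with continuity correction gives 73.5%, Fisher's exact test 74.1% and the uncorrected formula 78.9%. The stated figure is reproduced with the correction. The uncorrected formula is used below because only the comparison between sets matters.

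**Inputs.** n = 80 per arm and two-sided 5% come from the documents. The share q of the FAS at or above the threshold is an assumption, and so are the rates p1 and p2 among patients able to respond. The BICLA rates serve as one illustration. In practice q differs by threshold and is lower for SRI-10 than for SRI-8.

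**Effect size.** The FAS rates are q·p1 and q·p2, so the FAS risk difference is q·(p2 − p1):

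- q = 0.8: 0.8 × 20 = 16 points
- q = 0.6: 0.6 × 20 = 12 points
- q = 0.5: 0.5 × 20 = 10 points

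With 20.6% vs 40.6%, the odds ratio of 2.63 becomes 2.44, 2.28 and 2.22 respectively. The risk ratio does not change, because q cancels.

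**Power.** Power = Φ[(d − 1.96·SE0)/SE1], where d is the difference in rates, SE0 = √[2p̄(1−p̄)/n], p̄ is the mean of the two rates, and SE1 = √{[p1(1−p1) + p2(1−p2)]/n}. The whole FAS uses rates q·p1 and q·p2 with n = 80. The restricted set uses p1 and p2 with n = 80q.

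Example, q = 0.6, 20.6% vs 40.6%:

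- Whole FAS: rates 0.1236 and 0.2436, d = 0.12, SE0 = 0.0612, SE1 = 0.0605. Power = Φ(0.000) = 50.0%.
- Restricted, n = 48: d = 0.20, SE0 = 0.0941, SE1 = 0.0918. Power = Φ(0.170) = 56.8%.

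| Rates if able to respond | All able (q = 1) | q = 0.8: FAS / restricted | q = 0.6: FAS / restricted |
|---|---|---|---|
| 5% vs 15% | 56.0% | 46.2% / 47.0% | 35.8% / 37.0% |
| 10% vs 20% | 42.4% | 34.2% / 35.2% | 26.2% / 27.6% |
| 10% vs 25% | 70.8% | 59.1% / 61.0% | 45.8% / 48.9% |
| 20.6% vs 40.6% | 78.9% | 65.6% / 69.4% | 50.0% / 56.8% |
| 30% vs 50% | 73.7% | 58.4% / 63.9% | 42.7% / 51.6% |
| 40% vs 60% | 72.0% | 54.3% / 62.1% | 38.0% / 50.0% |

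The recoverable part is about 1 to 8 points at q = 0.8 and 1 to 12 points at q = 0.6. It is less than half of the total loss in every row. At 20.6% vs 40.6% and q = 0.6, for example, power falls by 28.9 points and restricting returns 6.8.

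The reason is that the FAS test statistic is about √[(1−p)/(1−qp)] times the restricted one, where p is the mean rate among those able to respond. At q = 0.6 and p = 0.306 this is √(0.694/0.8164) = 0.92. The penalty is small when response is rare and grows as response becomes common.

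**Cross-checks.** A simulated covariate-adjusted logistic model (80 per arm, 20.6% vs 40.6%, 1,500 runs) gave 63.1% vs 66.5% at q = 0.8 and 47.4% vs 56.2% at q = 0.6. With 89 per arm, the formula at q = 0.6 gives 54.3% vs 61.1%, a similar gap.

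**SRI-6.** Under the Week 0 recheck q should be close to 1. At q = 0.95 and 20.6% vs 40.6%, power is 75.9% vs 76.8%, a difference of about 1 point.

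**The case against.** The strongest reply is that nothing here is an error. The FAS difference is the effect in all randomised and dosed patients, its type I error is kept, and a common denominator keeps SRI-4, 6, 8 and 10 nested and comparable. Restricting gives each threshold its own population and answers a different question. This stands, and it is why the restricted analysis belongs beside the FAS result and should not replace it.

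The plan also has outputs that do not depend on a threshold: a t-test on the Week 36 change in the SELENA-SLEDAI score (SAP 5.2.4.3.4) and SLEDAI-2K change by arm (5.2.4.3.2). These help, but they do not show how many patients could have met SRI-8 or SRI-10.

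A reader might infer three stronger things that the documents do not support:

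- **That SRI-6 has the same problem.** Protocol 11.2 requires eligibility to be checked again at Week 0 before randomisation, and Protocol 10.9.2 lists SLEDAI-2K at that visit. A score below 6 should then arise only through a deviation, or because entry uses SLEDAI-2K while the SRI uses SELENA-SLEDAI. The documents size neither.
- **That a 20-point effect showing as 12 points means a correspondingly large avoidable loss of power.** Most of the loss comes from having fewer patients able to respond, and restricting does not restore them.
- **That the trial's conclusion is at risk.** Success rests on the IFN signature and BICLA (SAP 5.2.4.1). The named alternative endpoint is SRI-4, whose 4-point fall is possible for anyone scoring at least 6.

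**Conclusion.** The point holds for SRI-8 and SRI-10 as a matter of interpretation and modest efficiency. Patients at 6–7 or 6–9 are structural non-responders whom the plan does not separate. The absolute difference shrinks in proportion to the share able to respond, and the odds ratio shrinks less. With 80 per arm and the assumed rates above, the recoverable loss is about 1 to 12 power points if 60% can respond and 1 to 8 if 80% can.

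The actual size cannot be fixed from the documents, which give neither the baseline score distribution nor any SRI-6, 8 or 10 rate. The FAS analysis is valid, SRI-6 is essentially unaffected, and these are secondary analyses outside the success criterion. This is a cheap improvement to the plan.

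**What to change.** In SAP 5.2.4.3.1, add logistic regressions of SRI-8 in FAS patients with a baseline SELENA-SLEDAI of at least 8, and of SRI-10 in those with at least 10, using the same covariates. Present each beside its whole-FAS result and report the number eligible by arm. That count matters because the score is not a minimisation factor: at q = 0.6 with 80 per arm, the eligible shares could differ by chance by about 1.96 × √(2 × 0.6 × 0.4/80) = 15 percentage points. State the score fall that defines SRI-6, 8 and 10 in SAP 4.1.2.1. Because the subset is fixed before the first dose, the comparison between randomised arms is kept.

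The cost is a few lines of SAP text and two filtered runs before database lock. The downside is smaller denominators and a different population at each threshold, which the table titles should state.

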13.9.3 Analysis of the Clinical Secondary Endpoints

- The response to treatment according to response criteria described in section 13.3.1 will be analyzed using a logistic regression using the response rate as dependent variable and treatment as independent variable, while adjusting for the minimization factors used for randomization.
- The SRI-4, 6, 8, 10 response to treatment according to response criteria described in section 13.3.1 will be analyzed using a logistic regression using the response rate as dependent variable and treatment as independent variable, while adjusting for the minimization factors used for randomization.
- Number of patients achieving a SLEDAI response, defined as a reduction of the SLEDAI-2K score of at least 4 points at Week 36 compared to baseline will be analyzed using frequency table methods
- BILAG grade changes by body system will be analyzed using non-parametric Wilcoxon-test
- Number of patients with an SLE flare (SELENA-SLEDAI flare index; BILAG flares) will be analyzed using frequency table methods
- Clinical response by assessing disease activity using: SELENA-SLEDAI, SLICC/ACR-DI, and Cutaneous LE Disease Area and Severity Index (CLASI) will be analyzed using a t-test

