2.2.2 Secondary objectives

The secondary objectives of this study are:

- To evaluate the efficacy of treatment with IFN-K using:
 - The SLE Responder Index [(SRI)-4 and above]
 - The SLE Disease Activity Index-2000 index (SLEDAI-2K)
 - The BILAG-2004 index
 - The Safety of Estrogen in Lupus Erythematosus National Assessment-SLEDAI (SELENA-SLEDAI) Flare index
 - The Systemic Lupus International Collaborating Clinics/American College of Rheumatology Damage Index for Systemic Lupus Erythematosus (SLICC/ACR-DI)
 - The Cutaneous Lupus Erythematosus Disease Area and Severity Index (CLASI) in patients with cutaneous lesions at baseline
- To evaluate the immune response induced by IFN-K:

Statistical Analysis Plan

Study Name: IFN-K-002

SAP version & date: v4, 18/Jun/2018

- Anti-IFN α antibody response
- Anti-IFN α antibody neutralizing capacities
- Anti-KLH antibody response
- To assess the safety of IFN-K emulsified with ISA 51 VG

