5.3 Statistical/Analytical issues

5.3.1 Adjustments for Covariates

All models ANCOVA, MMRM, Logistic regression) will be adjusted on the minimization factors used for randomization (Ethnic (see section 9 Derived data) Origin, Age group, Presence or absence of renal involvement according to the BILAG at screening, With or without CS treatment at screening, With or without HCQ treatment at screening, With or without MMF treatment at screening).

In addition, MMRM will be adjusted on the baseline value.

For “Ethnic origin”, the reclassified values (see section 9 Derived data) will be used for primary analysis. The values from the eCRF will be used for sensitivity analysis. In the same way, for “Presence or absence of renal BILAG at screening”, the re-computed renal BILAG score derived in the statistics analysis datasets will

Statistical Analysis Plan

Study Name: IFN-K-002

SAP version & date: v4, 18/Jun/2018

be used for primary analysis. The values from the eCRF will be used as sensitivity analysis. (Statistical tables 14.2.3.1.4 & 14.2.3.2.3)

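### SLEDAI-2K, a named secondary objective, is compared between arms only as an unadjusted 4-point responder table, and no full-scale SLEDAI comparison in the SAP is adjusted

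*SAP*

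**What the plan says.** SAP 2.2.2 lists "The SLE Disease Activity Index-2000 index (SLEDAI-2K") among the instruments for the secondary efficacy objective. Protocol 11.6 describes a score from 0 to 105, and the schedule collects it at screening and at Weeks 0, 12, 24 and 36.

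SAP 5.2.4.3.2 handles it in two ways. The 4-point reduction at Week 36 "compared to baseline will be analyzed using frequency table methods" (Table 14.2.9). The full scale is tabulated only: "SLEDAI-2K score at each visit and change from baseline by treatment group will also be presented" (Tables 14.2.10.1 and 14.2.10.2).

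Covariate adjustment is set in SAP 5.3.1: "All models ANCOVA, MMRM, Logistic regression) will be adjusted on the minimization factors used for randomization". A frequency table or a t-test is not among those models. BICLA and SRI-4, 6, 8 and 10 are analysed by logistic regression and so are adjusted.

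For the SELENA-SLEDAI total score, SAP 5.2.4.3.4 says "The change at Week 36 will be analyzed using a t-test. (Statistical tables 14.2.14.1 to 14.2.14.2"). Protocol 13.9.3 agrees: "Clinical response by assessing disease activity using: SELENA-SLEDAI, SLICC/ACR-DI, and Cutaneous LE Disease Area and Severity Index (CLASI) will be analyzed using a t-test".

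**The concern.** The treatment of SLEDAI-2K is out of line with the rest of the section. The BILAG global score has a Wilcoxon test of change. SELENA-SLEDAI, SLICC/ACR-DI and both CLASI scores have t-tests of change. SLEDAI-2K is the one numeric secondary score whose change has no named test, and SAP section 7 gives no reason. Among the responder endpoints, BICLA and the SRI family are adjusted for the minimisation factors, while the SLEDAI response is not.

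A responder cut treats a 12-point fall like a 4-point fall, and a 2-point improvement like a worsening. If the drug shifts scores across the whole range, the cut discards information and a real effect is more likely to be missed. SLEDAI-2K is also the version of the score that enters BICLA and LLDAS, so a clear estimate of its change would help in reading those composites.

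**Working it through.** **1. The plan's own figures.** With 80 evaluable patients per arm and two-sided 5% (SAP 2.3.2, 5.1.2):
- IFN signature, difference 32.6, SD 68: noncentral-t power 85.4% (stated: 85%).
- BICLA, 20.6% vs 40.6%: 78.9% uncorrected, 73.5% with continuity correction, 74.1% by Fisher's exact test (stated: 73%). The stated figure fits a corrected or exact test.

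No SD, effect or response rate is given for SLEDAI-2K. Everything below therefore rests on assumed values.

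**2. Cost of the cut under a uniform normal shift.** Assume normal change scores with equal SDs and response rates p0 (placebo) and p1 (IFN-K).
- Standardised difference: d = z(p1) − z(p0).
- t-test: noncentral t, 158 df, noncentrality d·√(80/2).
- Two proportions, uncorrected: Φ{[|p1−p0|√80 − 1.96√(2p̄q̄)] / √(p0q0+p1q1)}.

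Worked case, 40% vs 60%: d = 0.253 + 0.253 = 0.507 (unrounded inputs). The binary test gives Φ[(1.789 − 1.386)/0.693] = Φ(0.58) = 72.0%. The t-test gives 89.0%. The loss is 17.0 points.

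| p0 vs p1 | d | t-test | binary | loss (points) |
|---|---|---|---|---|
| 20.6% vs 40.6% (BICLA rates, borrowed) | 0.583 | 95.6% | 78.9% | 16.6 |
| 30% vs 50% | 0.524 | 90.9% | 73.7% | 17.2 |
| 40% vs 60% | 0.507 | 89.0% | 72.0% | 17.0 |
| 40% vs 55% | 0.379 | 66.4% | 47.6% | 18.8 |
| 50% vs 65% | 0.385 | 67.8% | 48.4% | 19.5 |
| 30% vs 45% | 0.399 | 70.8% | 50.0% | 20.8 |

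Losses were taken before rounding.

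Setting the scale directly (SD 4 to 6, mean difference 1.5 to 2.5, placebo mean drop 2 to 5) gives losses from 9.9 points (97.6% vs 87.6%) to 21.6 points (74.5% vs 52.9%). That is the range of about 10 to 22. With a continuity-corrected test, the 20-point cases in the table lose 22 to 23. The SAP does not name the test, so this choice is open.

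**3. Sensitivity to effect shape.** Simulation with 80 per arm, SD 4, change rounded to even points, placebo response 20.6%, uncorrected chi-square vs t-test:
- Uniform shift to 40.6%: 80% vs 95%, a loss of 15.
- 40% of treated patients gain 6 points and the rest gain nothing: 86% vs 92%, a loss of about 6.
- The effect only moves non-responders to drops of 4 to 6 points, reaching 40.6%: 79% vs 52%. Here the cut is the stronger test.

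**4. The two SLEDAI scores.** Protocol Appendices 2 and 4 print the same 24 descriptors with the same weights and the same 10-day window. SAP section 9 scores both by summing weights. The SAP lists them as separate secondary instruments with separate tables and nowhere says that one analysis stands in for the other.

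**5. Protocol 13.9.3.** Its first bullet reads "The response to treatment according to response criteria described in section 13.3.1 will be analyzed using a logistic regression" with adjustment for the minimisation factors, and 13.3.1 includes the SLEDAI response. Its third bullet names the SLEDAI response and assigns it to a frequency table. The SAP follows the third bullet.

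**The case against.** The strongest reply is that the trial already tests a full-scale SLEDAI change. The SELENA-SLEDAI t-test uses, as printed, the same items and weights at the same Week 36 visit, so a second test would overlap heavily. This stands. A reader might infer that the trial gives up all full-scale SLEDAI power, and the documents do not support that. What remains is that the existing test is unadjusted and the named SLEDAI-2K objective has no test of its own.

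A reader might also infer that the SAP departs from the protocol by using a frequency table. It does not, because the third bullet of 13.9.3 is specific to this endpoint. In 13.3.1 the term for response criteria is attached to SRI-4, so the first bullet may never have been meant to reach the SLEDAI response. Against that, the second bullet already covers SRI-4, which leaves the first bullet with little else to govern. The wording needs reconciling.

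SAP 5.1.2 promises 95% confidence intervals for differences in means on continuous endpoints. Read broadly, that covers SLEDAI-2K change and carries the information of an unadjusted test, though 5.2.4.3.2 does not call for it in its tables. Adjustment would still be new.

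Finally, the 4-point response is the protocol-defined endpoint, and SRI-4 uses a drop of the same size ("points in SELENA-SLEDAI at week 36 compared with baseline"). The adjusted SRI-6, 8 and 10 analyses partly credit larger falls. Trial success rests on the IFN signature and BICLA. These points limit the severity.

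**Conclusion.** The point holds as a minor one. SLEDAI-2K is compared only through an unadjusted 4-point table, its change has no named test, and no full-scale SLEDAI comparison in the SAP is adjusted for baseline or the minimisation factors.

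The power cost of the cut is roughly 10 to 22 points with 80 per arm, an uncorrected binary test and an assumed uniform normal shift. It falls to about 6 points if a subset drives the effect, and the order reverses if the effect only carries non-responders just past the cut. A single figure such as 16 to 18 points might be read as a property of this trial. It is not, because it depends on borrowed or assumed response rates and on the assumed shape. The gain from adjustment cannot be sized either, since the documents give no correlation between baseline, the minimisation factors and the Week 36 score.

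**What to change.** In SAP 5.2.4.3.2, before unblinding:

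- **(a)** Pre-specify an ANCOVA of Week 36 SLEDAI-2K on treatment, Week 0 SLEDAI-2K and the six minimisation factors. Report the adjusted difference with its 95% confidence interval in Table 14.2.10.2.
- **(b)** Add to the 4-point response the same adjusted logistic regression as SRI-4, for consistency with the other responder endpoints. Keep the frequency table in 14.2.9 and name any test used there.
- **(c)** Reconcile the first and third bullets of Protocol 13.9.3 and record the decision in SAP 7.2.2.

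At the least, the SAP should state that the SELENA-SLEDAI analysis is meant to serve for SLEDAI-2K change.

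The cost is SAP wording and two models on data already collected. The downside is one or two more secondary p-values, partly overlapping the SELENA-SLEDAI test. The testing sequence in SAP 5.3.5 covers only the co-primary endpoints and is unaffected.

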13.3 Secondary Endpoints

13.3.1 Clinical Secondary Endpoints

- Response to treatment with IFN-K, as measured by the SLE Responder Index (SRI)-4 response criteria at Week 36:
 - Reduction ≥ 4 points in SELENA-SLEDAI
and
 - No new BILAG A
and
 - No more than 1 new BILAG B
and
 - No deterioration in PGA (< 10% worsening) on VAS 100 mm compared with baseline
- Response to treatment with IFN-K, as measured by SLEDAI response, defined as a reduction of the SLEDAI-2K score of at least 4 points at Week 36 compared to baseline
- Response to treatment with IFN-K, as measured by BILAG grade changes by body system
- Response to treatment with IFN-K, as measured by Incidence of SLE flare (SELENA SLEDAI flare index. BILAG flares)
- Response to treatment with IFN-K, as measured by SLICC/ACR-DI
- Response to treatment with IFN-K, as measured by Cutaneous LE Disease Area and Severity Index (CLASI)

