14.2.5.11	Secondary efficacy analysis - Composite SRI-4 response (CS 7.5 mg) - Logistic regression model with status of IFN α neutralizing antibodies (positive/negative) at Week 36 as dependent variable				X	
14.2.6.1	Secondary efficacy analysis - SRI-6 response at Week 36			X		
14.2.6.2	Secondary efficacy analysis - SRI-6 response at Week 36 - Logistic regression model			X		

Statistical Analysis Plan

Study Name: IFN-K-002

SAP version & date: v4, 18/Jun/2018

Number	Title	Screened	SAF	FAS	PP	Other
14.2.7.1	Secondary efficacy analysis - SRI-8 response at each visit			X		
14.2.7.2	Secondary efficacy analysis - SRI-8 response at Week 36 - Logistic regression model			X		
14.2.8.1	Secondary efficacy analysis - SRI-10 response at each visit			X		
14.2.8.2	Secondary efficacy analysis - SRI-10 response at Week 36 - Logistic regression model			X		
14.2.9	Secondary efficacy analysis - SLEDAI response at week 36			X		
14.2.10.1	Secondary efficacy analysis - SLEDAI-2K scores - Value at each visit			X		
14.2.10.2	Secondary efficacy analysis - SLEDAI-2K scores - Change from baseline			X		
14.2.11	Secondary efficacy analysis - BILAG - Shift table			X		
14.2.12	Secondary efficacy analysis - BILAG global score			X		
14.2.13	Secondary efficacy analysis - SELENA-SLEDAI - Mild, moderate or severe SLE flare			X		
14.2.14.1	Secondary efficacy analysis - SELENA-SLEDAI score - Value at each visit			X		
14.2.14.2	Secondary efficacy analysis - SELENA-SLEDAI score - Change from baseline			X		
14.2.15.1	Secondary efficacy analysis - SLICC/ACR-DI score - Value at each visit			X		
14.2.15.2	Secondary efficacy analysis - SLICC/ACR-DI score - Change from baseline			X		
14.2.16.1	Secondary efficacy analysis - CLASI - Total activity score - Value at each visit			X		
14.2.16.2	Secondary efficacy analysis - CLASI - Total activity score - Change from baseline			X		
14.2.17.1	Secondary efficacy analysis - CLASI - Total damage score - Value at each visit			X		
14.2.17.2	Secondary efficacy analysis - CLASI - Total damage score - Change from baseline			X		
14.2.18	Secondary efficacy analysis - LLDAS			X		
14.2.19	Immunogenicity analysis - Anti-IFN α binding antibody titers - Positive antibody response over time				X	
14.2.20	Immunogenicity analysis - Log-transformed dilution titers for anti-IFN α binding antibodies				X	

Statistical Analysis Plan

Study Name: IFN-K-002

SAP version & date: v4, 18/Jun/2018

Number	Title	Screened	SAF	FAS	PP	Other

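### The SAP moves the BILAG Wilcoxon test from grade change by body system to a summed global score, leaving a retained secondary endpoint without an inferential between-arm comparison, and SAP 7.2.2 does not declare it

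*SAP*

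**What the plan says.** Protocol 13.3.1 lists this clinical secondary endpoint: "Response to treatment with IFN-K, as measured by BILAG grade changes by body system". Protocol 13.9.3 fixes its analysis: "BILAG grade changes by body system will be analyzed using non-parametric Wilcoxon-test". It gives no time point and no coding of the grades.

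SAP 4.1.2.1 keeps the endpoint, "as measured by BILAG grade changes by body system". SAP 5.2.4.3.3 then plans two outputs:

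- By system: "Shift tables between Baseline and LVA (last available value between Week 36 and Week 24) will also be presented for each body system" (Table 14.2.11). No test is attached and treatment group is not mentioned.
- Global score: "descriptive statistics for the BILAG global score at each visit and change from baseline to LVA will be presented", followed directly by "The difference between treatment groups for the change from baseline to LVA will be analyzed using the non-parametric Wilcoxon-test" (Table 14.2.12). SAP 10.1 titles that table "Secondary efficacy analysis - BILAG global score".

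The global score is 12 per grade A, 8 per grade B and 1 per grade C, with D and E scored 0, added over nine systems: "Where A, B and C represent the number of Grades A, B and C respectively at each assessment".

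Protocol Section 13 says that major departures from the planned analysis, with their reasons, will be described in the SAP. SAP 7.2.2 lists the added composite SRI-4 and the removed lupus-therapy analysis. It does not mention BILAG.

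**The concern.** The endpoint asks in which organ systems IFN-K changes disease grade. A single sum over nine systems answers another question: whether total weighted activity differs between arms. Improvement in one system can offset worsening in another, so a difference on the sum does not locate the effect, and no difference on the sum does not exclude opposite effects in two systems.

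What is at stake is the interpretation of one secondary endpoint. A reader of the study report would find a p-value under BILAG and could take it as the analysis that the protocol specified, when it tests a different variable.

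**Working it through.** The documents give no power or alpha figure specific to this endpoint, so there is no stated figure to reproduce. The check is a comparison of the texts, followed by arithmetic on the SAP's own weights.

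**1. The texts side by side**

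| Item | Protocol | SAP |
|---|---|---|
| Endpoint | Grade change by body system (13.3.1) | Same (4.1.2.1) |
| By-system analysis | Wilcoxon test (13.9.3) | Shift table, arm not mentioned (5.2.4.3.3, Table 14.2.11) |
| Wilcoxon test applied to | Grade change by body system | Global score, baseline to last available value (Table 14.2.12) |
| Declared as a change | Promised for major departures (Section 13) | Not in 7.2.2 |

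The table list in SAP 10.1 contains no by-system BILAG test. Elsewhere in SAP 5.2.4.3 the SLEDAI-2K outputs are expressly by treatment group, whereas the shift-table sentence is silent on this.

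**2. What the sum can hide**

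The change in one system is the weight at follow-up minus the weight at baseline, with A = 12, B = 8, C = 1, D = E = 0. The change in the score is the sum over systems.

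- B to A in one system: 12 - 8 = +4. B to C in another: 1 - 8 = -7. Net +4 - 7 = -3, scored as improvement although one system reached grade A. Two grade Bs are enough to meet inclusion criterion 3, so this baseline is an ordinary one.
- C to A with A to C: +11 - 11 = 0.
- B to A with A to B: +4 - 4 = 0.

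Listing every pair of one worsening and one improving system gives 15 pairs that cancel exactly, and 8 pairs in which a worsening to grade A still nets an improvement. Protocol 11.6 defines grade E as no current or previous activity, so an active system cannot move into E. Leaving out moves into E removes 6 and 3 pairs: 15 - 6 = 9 and 8 - 3 = 5.

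**3. Illustration with assumed rates**

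The rates here are assumptions, chosen to oppose each other exactly. System 1 improves from B to C in 20.6% of placebo and 40.6% of IFN-K patients. System 2 worsens from C to B in 10% and 30%. The expected change in the score is the same in both arms:

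- Placebo: 7 × (0.10 - 0.206) = -0.742
- IFN-K: 7 × (0.30 - 0.406) = -0.742

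With 80 patients per arm, 2000 simulated trials and two-sided 5% Wilcoxon tests, the by-system tests reject in about 80% (system 1) and 90% (system 2) of trials. The global-score test rejects in about 5%, its significance level. This shows that cancellation can happen. It does not show that it is likely.

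**4. Multiplicity if the tests are restored**

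Nine tests at 5%, if independent, have a family-wise error of 1 - 0.95^9 = 0.37. A Bonferroni level would be 0.05 / 9 = 0.0056.

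**The case against.** The case against making much of this is substantial, and most of it stands.

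- **A comparison of some kind remains.** A reader might infer that the endpoint now has no comparison at all. The documents do not support that: shift tables for each system are still planned. What is lost is inference, and also any assurance that the tables are split by arm.
- **Organ worsening is counted elsewhere.** A reader might infer that worsening in one organ disappears from the trial. It does not. It enters BICLA and SRI-4 through their limits on new A and B grades, LLDAS through any BILAG item recorded as new, and time to first flare, which is compared by Cox regression. The patient above with B to A fails BICLA, because a baseline B did not improve. These endpoints pool the systems, however, so none of them shows which organ differs between arms.
- **Not every offset is perverse.** A to C with one new B elsewhere also nets -3 (-11 + 8), but that pattern meets the BILAG parts of both BICLA and SRI-4. It is not worsening by the trial's own standard.
- **The unequal steps are not a defect.** A to B counts -4 and B to C counts -7 because the SAP uses a published numerical scheme, which it cites.
- **The restored tests have limits.** Entry needs only one A or two Bs, and renal A and neuropsychiatric A are excluded, so some systems may have few active patients and many ties. The protocol's single line leaves coding and time point open. This could have justified the switch, but neither SAP 5.2.4.3.3 nor 7.2.2 gives such a reason.
- **The change could be declared elsewhere.** The SAP's version history is incomplete in the public copy. The statement about non-declaration is therefore limited to Section 7.

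**Conclusion.** The point holds at the level of one secondary endpoint. A pre-specified by-system comparison has been replaced by a test of a different variable. The retained endpoint has no between-arm test in any of the nine systems, and SAP 7.2.2 is silent. Under the SAP's weights the replacement can score a net improvement while one system moves to grade A.

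The weight arithmetic rests only on the SAP's definition. The 80%, 90% and 5% figures rest on constructed rates and are not a forecast.

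A reader might go further and infer a threat to the trial's conclusion. The documents do not support that: the study is judged positive on the gene signature and BICLA, and neither uses the global score. The change is still worth making, because it uses data already collected and gives the endpoint the answer that the protocol promised.

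**What to change.** In SAP 5.2.4.3.3:

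1. State that Table 14.2.11 is presented by treatment group.
2. Restore the protocol's Wilcoxon test for each body system, on ordinal grade change from baseline to the last available value. State the grade coding, including whether A to B and B to C count as equal steps and how D and E are treated.
3. Report nominal p-values, labelled as unadjusted for multiplicity, and note that systems with few active patients will be uninformative.
4. Keep the global-score Wilcoxon test (Table 14.2.12) as an added analysis.

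In SAP 7.2.2, declare the global-score analysis as an addition to the protocol, with the reason.

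The cost is one further output table, a coding rule and a few lines of text. No new data are needed. The drawback is nine nominal tests that can support no formal claim, which the labelling makes plain.
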